**Arm B (up to n=16 maximum enrolled):**

**Participants will be sequentially assigned to groups B.1 and B.2. Once 4 men complete their biopsy visits for subgroup B.1, subsequent men will be enrolled into sub-group B.2. A total of 8 men must complete all study visits for this arm.**

**Group B.1 (n=8; enrollment will close once 4 men complete their biopsy visit):**

**Visit 1(screening):** Eligible MSM will provide written informed consent, be questioned about their medical history, undergo a physical exam (conducted by a study clinician) a rapid HIV test, and a peripheral blood sample for a complete blood count, creatinine, coagulation test, and hepatitis B. Participants will then be asked to return within 1- 6 weeks for visit 2.

**Visit 2:** Participants will be given a one- day supply of Genvoya®. Staff will provide instructions to participant on when to take dose at home. Participants will be asked to dose **24hrs before visit 3** and will be instructed to videotape or photograph themselves taking dose with the timestamp included. Study staff will instruct participants to bring the video/photo to their next visit to provide proof of dosing. Participants will also have the option to send a text to a specified number with the time and date of dose if their phone device does not have video capabilities.

**Visit 3:** Visit 3 takes place 24hrs after home dose. During this visit, drugs will be dispensed to participants, and they will be instructed to take one dose of Genvoya®. Men will be dosed on-site (time of dose will be recorded) and asked to return in 4hrs. Procedures should be done as close to 4hrs as possible with a +/- 1 hour window.

**Visit 4:** Visit 4 takes place 4hrs (+/- 1 hour) after on-site dose. Approximately 24 mL of blood will be drawn, an oral cheek swab, 1 pre- wet penile swabs and 1 dry penile swab, and a urethral swab will be collected. After previous swab collections are complete, participants will be asked to provide a urine sample, some of which will be used for gonorrhea and chlamydia testing, then the practitioner (Principal investigator or Co- investigator) will collect rectal secretion samples by using two swabs and insert an aptima swab for rectal gonorrhea and chlamydia testing, before the participant undergoes a rectal biopsy via rigid sigmoidoscopy.

Participants will be asked to provide an optional single semen sample, which will be collected at home, no more than 2hrs before/after the biopsy visit.

**Visit 5:** Visit 5 takes place 72hrs (+/- 1 hour) after on-site dose. Approximately 24 mL of blood will be drawn, an oral cheek swab, 1 pre- wet penile swabs and 1 dry penile swab, and a urethral swab will be collected. After previous swab collections are complete, participants will be asked to provide a urine sample.

**Group B.2 (n=8; enrollment will close once 4 men complete their biopsy visit):**

**Visit 1(screening):** Eligible MSM will provide written informed consent, be questioned about their medical history, undergo a physical exam (conducted by a study clinician) a rapid HIV test, and a peripheral blood sample for a complete blood count, creatinine, coagulation test, and hepatitis B. Participants will then be asked to return within 1- 6 weeks for visit 2.

**Visit 2:** Participants will be given a one- day supply of Genvoya®. Staff will provide instructions to participant on when to take dose at home. Participants will be asked to dose **24hrs before visit 3** and will be instructed to videotape or photograph themselves taking dose with the timestamp included. Study staff will instruct participants to bring the video/photo to their next visit to provide proof of dosing. Participants will also have the option to send a text to a specified number with the time and date of dose if their phone device does not have video capabilities.

**Visit 3:** Visit 3 takes place 24hrs after home dose. During this visit, drugs will be dispensed to participants, and they will be instructed to take one dose of Genvoya®. Men will be dosed on-site (time of dose will be recorded) and asked to return in 4hrs. Procedures should be done as close to 4hrs as possible with a +/- 1 hour window.

**Visit 4:** Visit 4 takes place 4hrs (+/- 1 hour) after on-site dose. Approximately 24 mL of blood will be drawn, an oral cheek swab, 1 pre- wet penile swabs and 1 dry penile swab, and a urethral swab will be collected. After previous swab collections are complete, participants will be asked to provide a urine sample.

**Visit 5:** Visit 5 takes place 72hrs (+/- 1 hour) after on-site dose. Approximately 24 mL of blood will be drawn, an oral cheek swab, 1 pre- wet penile swabs and 1 dry penile swab, and a urethral swab will be collected. After previous swab collections are complete, participants will be asked to provide a urine sample, some of which will be used for gonorrhea and chlamydia testing, then the practitioner (Principal investigator or Co- investigator) will collect rectal secretion samples by using two swabs and insert an aptima swab for rectal gonorrhea and chlamydia testing, before the participant undergoes a rectal biopsy via rigid sigmoidoscopy.

TITLE OF PROJECT: On-Demand PEP  
Emory IRB  
PRINCIPAL INVESTIGATOR: [name], MPH

Participants will be asked to provide an optional single semen sample, which will be collected at home, no more than 2hrs before/after the biopsy visit.

**Arm C (up to n=16 maximum enrolled):**

**Participants will be sequentially assigned to groups C.1 and C.2. Once 4 men complete their biopsy visits for subgroup C.1, subsequent men will be enrolled into sub-group C.2. A total of 8 men must complete all study visits for this arm.**

**Group C.1 (n=8; enrollment will close once 4 men complete their biopsy visit):**

**Visit 1(screening):** Eligible MSM will provide written informed consent, be questioned about their medical history, undergo a physical exam (conducted by a study clinician) a rapid HIV test, and a peripheral blood sample for a complete blood count, creatinine, coagulation test, and hepatitis B. Participants will then be asked to return within 1- 6 weeks for visit 2.

**Visit 2:** Participants will be given a one- day supply of Genvoya®. Staff will provide instructions to participant on when to take dose at home. Participants will be asked to dose **24hrs before visit 3** and will be instructed to videotape or photograph themselves taking dose with the timestamp included. Study staff will instruct participants to bring the video/photo to their next visit to provide proof of dosing. Participants will also have the option to send a text to a specified number with the time and date of dose if their phone device does not have video capabilities.

**Visit 3:** Visit 3 takes place 24hrs after home dose. During this visit, drugs will be dispensed to participants, and they will be instructed to take one dose of Genvoya®. Men will be dosed on-site (time of dose will be recorded) and asked to return in 24hrs. Procedures should be done as close to 24hrs as possible with a +/- 1 hour window.

**Visit 4:** Visit 4 takes place 24hrs (+/- 1 hour) after on-site dose. Approximately 24 mL of blood will be drawn, an oral cheek swab, 1 pre- wet penile swabs and 1 dry penile swab, and a urethral swab will be collected. After previous swab collections are complete, participants will be asked to provide a urine sample, some of which will be used for gonorrhea and chlamydia testing, then the practitioner (Principal investigator or Co- investigator) will collect rectal secretion samples by using two swabs and insert an aptima swab for rectal gonorrhea and chlamydia testing, before the participant undergoes a rectal biopsy via rigid sigmoidoscopy.

Participants will be asked to provide an optional single semen sample, which will be collected at home, no more than 2hrs before/after the biopsy visit.

**Visit 5:** Visit 5 takes place 96hrs (+/- 1 hour) after on-site dose. Approximately 24 mL of blood will be drawn, an oral cheek swab, 1 pre- wet penile swabs and 1 dry penile

TITLE OF PROJECT: On-Demand PEP  
Emory IRB  
PRINCIPAL INVESTIGATOR: [name], MPH

swab, and a urethral swab will be collected. After previous swab collections are complete, participants will be asked to provide a urine sample.

**Group C.2 (n=8; enrollment will close once 4 men complete their biopsy visit):**

**Visit 1(screening):** Eligible MSM will provide written informed consent, be questioned about their medical history, undergo a physical exam (conducted by a study clinician) a rapid HIV test, and a peripheral blood sample for a complete blood count, creatinine, coagulation test, and hepatitis B. Participants will then be asked to return within 1- 6 weeks for visit 2.

**Visit 2:** Participants will be given a one- day supply of Genvoya®. Staff will provide instructions to participant on when to take dose at home. Participants will be asked to dose **24hrs before visit 3** and will be instructed to videotape or photograph themselves taking dose with the timestamp included. Study staff will instruct participants to bring the video/photo to their next visit to provide proof of dosing. Participants will also have the option to send a text to a specified number with the time and date of dose if their phone device does not have video capabilities.

**Visit 3:** Visit 3 takes place 24hrs after home dose. During this visit, drugs will be dispensed to participants, and they will be instructed to take one dose of Genvoya®. Men will be dosed on-site (time of dose will be recorded) and asked to return in 24hrs. Procedures should be done as close to 24hrs as possible with a +/- 1 hour window.

**Visit 4:** Visit 4 takes place 24hrs (+/- 1 hour) after on-site dose. Approximately 24 mL of blood will be drawn, an oral cheek swab, 1 pre- wet penile swabs and 1 dry penile swab, and a urethral swab will be collected. After previous swab collections are complete, participants will be asked to provide a urine sample.

**Visit 5:** Visit 5 takes place 96hrs (+/- 1 hour) after on-site dose. Approximately 24 mL of blood will be drawn, an oral cheek swab, 1 pre- wet penile swabs and 1 dry penile swab, and a urethral swab will be collected. After previous swab collections are complete, participants will be asked to provide a urine sample, some of which will be used for gonorrhea and chlamydia testing, then the practitioner (Principal investigator or Co- investigator) will collect rectal secretion samples by using two swabs and insert an aptima swab for rectal gonorrhea and chlamydia testing, before the participant undergoes a rectal biopsy via rigid sigmoidoscopy.

Participants will be asked to provide an optional single semen sample, which will be collected at home, no more than 2hrs before/after the biopsy visit.

**Arm D (n=8; enrollment will close once 4 men complete their biopsy visit):**

**Visit 1 (screening):** Eligible MSM will provide written informed consent, be questioned about their medical history, undergo a physical exam (conducted by a study clinician) a rapid HIV test, and a peripheral blood sample for a complete blood count, creatinine, coagulation test, and hepatitis B. Participants will then be asked to return within 1- 6 weeks for visit 2.

**Visit 2:** Participants will be given a one- day supply of Genvoya®. Staff will provide instructions to participant on when to take dose at home. Participants will be asked to dose **24hrs before visit 3** and will be instructed to videotape or photograph themselves taking dose with the timestamp included. Study staff will instruct participants to bring the video/photo to their next visit to provide proof of dosing. Participants will also have the option to send a text to a specified number with the time and date of dose if their phone device does not have video capabilities.

**Visit 3:** Visit 3 takes place 24hrs after home dose. During this visit, drugs will be dispensed to participants, and they will be instructed to take one dose of Genvoya®. Men will be dosed on-site (time of dose will be recorded) and asked to return in 8hrs. Procedures should be done as close to 8hrs as possible with a +/- 1 hour window.

**Visit 4:** Visit 4 takes place 8hrs (+/- 1 hour) after on-site dose. Approximately 24 mL of blood will be drawn, an oral cheek swab, 1 pre- wet penile swabs and 1 dry penile swab, and a urethral swab will be collected. After previous swab collections are complete, participants will be asked to provide a urine sample, some of which will be used for gonorrhea and chlamydia testing, then the practitioner (Principal investigator or Co- investigator) will collect rectal secretion samples by using two swabs and insert an aptima swab for rectal gonorrhea and chlamydia testing, before the participant undergoes a rectal biopsy via rigid sigmoidoscopy.

Participants will be asked to provide an optional single semen sample, which will be collected at home, no more than 2hrs before/after the biopsy visit.

All participants will be asked to abstain from receptive anal intercourse for three days prior to drug dosing and during the study protocol in order to limit additional exposures (e.g. semen, douching, additional lubricants) to the rectal mucosa.

All participants who will undergo a rectal biopsy will be informed not to place anything into the rectum and abstain from intercourse 7 days after their rectal biopsy procedure to allow the mucosa to heal. If tested positive for gonorrhea and/or chlamydia, participant will be notified and referred to linkage for treatment.

*Biologic specimens:*

TITLE OF PROJECT: On-Demand PEP  
Emory IRB  
PRINCIPAL INVESTIGATOR: [name], MPH

Biologic specimens collected after the screening visit will be transferred directly to CDC for measurement of study drug levels. Specimens will be labeled with a unique ID that only the Emory study team will be able to link to identifiable information. CDC personnel will not have access to identifiable information.

*Contingency visit:*

Attempts to ensure adherence to the study visits will be made with telephone and/or email reminders to the participant. However, if for example, screening laboratory results are lost or are inconclusive or if a participant has been unable to adhere to study protocol, he may be rescheduled for a future date where the above visit procedures will be performed. These additional visits will be scheduled within the above visit windows.

*Timing of procedures after dose:*

The procedures conducted after dose, particularly those less than 24 hours after dose, should occur as close to the scheduled time points as possible. Protocol deviations will be filed for visits that occur outside of the target windows identified above only if the visit is conducted more than 3 hours beyond the target window defined above for each arm and visit.

*Phone calls/retention contacts:*

While on study, periodic phone calls, texts, or email reminders will occur between study staff and participants to ensure proper retention and adherence to study protocol.

Rectal biopsy procedures

All rectal biopsies will be performed utilizing a disposable rigid sigmoidoscope, light source, and jumbo biopsy forceps. [name] was trained in office based rectal biopsy procedures by [name], an experienced gastroenterologist at Emory University. All biopsies will be completed by either the PI or a delegated, licensed medical professional whom the PI has trained in the procedure. All biopsy procedures will be performed in an examination room at the Hope Clinic with assistance from the project coordinator or clinical research nurse. Similar procedures have been performed by [name] >300 times for other research protocols with no complications. Briefly, without the administration of any previous enemas or other preparation, 8-10 adequate ~1.0 mm thick biopsy specimens will be taken from normal-appearing rectal mucosa 10 cm above the external anal aperture using a rigid sigmoidoscope and flexible sigmoidoscopic forceps mounted on a semi-flexible rod. All biopsy specimens will be coded with a unique numeric identifier such that the CDC laboratories that receive the

TITLE OF PROJECT: On-Demand PEP  
Emory IRB  
PRINCIPAL INVESTIGATOR: [name], MPH

specimens will be unable to link them back to the study participants. Specimens will be transported directly to CDC after the study visit.

Twenty-four to forty-eight hours after the procedure, study personnel will contact the subjects who donated rectal biopsy samples and inquire about symptoms, complications, or adverse events related to study procedures. Subjects who report symptoms suggestive of any significant complications will receive advice on seeking care, and will be given referrals to appropriate healthcare professionals as needed. This follow-up may be completed over the phone or through electronic communication.

#### Semen collection:

After participants have taken study dose in clinic, they will be asked to obtain an optional semen sample 2hrs before or after the scheduled rectal biopsy or procedure visit. The semen will be collected by the participant at home using a provided collection cup and will be stored on ice until it is brought to the clinic. Participant will be provided towelettes for cleaning the head of the penis before masturbation is started. The sample should be collected no more than 2 hours before delivery to the clinic. The participant will be instructed to refrain from ejaculating, putting lubricants or saliva on their penis, or having insertive vaginal, anal or oral sex for at least 48 hours prior to semen collection. If these instructions are not followed, the semen sample can still be accepted.

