sequentially assigned to, the participant will be asked to return to the Hope Clinic at different time points to complete the remaining visits (visit 4 and visit 5). During visits 4 and 5, all participants will undergo blood collection (approximately 24 mL of blood will be obtained), an oral cheek swab, urethral swab, 1 pre-wet and 1 dry penile swabs, and a urine sample will be collected, some of which will be used for STI testing. Each participant will also undergo a single time-point (depending on study arm assignment—either visit 4 or 5) rectal secretion collection with swabs and wicks, a swab for rectal STI testing, and a rectal biopsy via rigid sigmoidoscopy. All participants will be asked to abstain from receptive anal intercourse for 7 days after biopsy procedures to allow the mucosa to heal.

Participants will also be asked to provide an optional single semen specimen on the day of rectal sampling to further evaluate drug levels. All biologic specimens will be transferred to CDC within 4 hours of collection for measurement of antiretroviral drug levels.

Participants may participate in more than one study arm; however, at least 6 weeks must lapse after completion of 1 study arm before entry into another. Men who participate in more than one arm will not be consented again and do not have to repeat the screening visit (visit 1) when starting another arm; they will begin the new arm at visit 2.

**Duration:** The duration of this study is 2 years. Participants will be considered ‘on-study’ for no more than 12 weeks.

**Sample size:** For this protocol we will recruit 62 HIV-negative MSM (age 18- 49) who meet eligibility criteria outlined in the protocol.

**Population:** The population to be studied in this protocol are healthy HIV negative MSM who are engaging in receptive anal intercourse (RAI) and are willing to perform study procedures. We will recruit participants through existing research databases at the Hope Clinic and the Rollins School of Public Health, through internet and paper advertisements, and community venues as is currently the process for [name] ongoing research protocols.

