**Pre-Drug Arm (up to n=6; enrollment for this Arm will close once 3 men complete their biopsy visit):**

**Visit 1 (screening):** Eligible MSM will provide written informed consent, be questioned about their medical history, undergo a physical exam (conducted by a study clinician) a rapid HIV test, and a peripheral blood sample for a complete blood count, creatinine, coagulation test, and hepatitis B. Participants will then be asked to return within 1- 6 weeks for visit 2.

**Visit 2:** Visit will occur within 1-6 weeks after the screening visit. Approximately 24 mL of blood will be drawn, an oral cheek swab, 1 pre- wet penile swabs and 1 dry penile swab, and a urethral swab will be collected. After previous swab collections are complete, participants will be asked to provide a urine sample, some of which will be used for gonorrhea and chlamydia testing, then the practitioner (Principal investigator or

TITLE OF PROJECT: On-Demand PEP  
Emory IRB  
PRINCIPAL INVESTIGATOR: [name], MPH

Co- investigator) will collect rectal secretion samples by using two swabs and insert an aptima swab for rectal gonorrhea and chlamydia testing, before the participant undergoes a rectal biopsy via rigid sigmoidoscopy.

Participants will be asked to provide an optional single semen sample, which will be collected at home, no more than 2hrs prior to or after the biopsy visit.

After 3 men complete the pre-drug arm, subsequent participants will be sequentially assigned to Arm A, B, C or D.

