**Visit 5:** Visit 5 takes place 48hrs (+/- 1 hour) after on-site dose. Approximately 24 mL of blood will be drawn, an oral cheek swab, 1 pre- wet penile swabs and 1 dry penile swab, and a urethral swab will be collected. After previous swab collections are complete, participants will be asked to provide a urine sample.

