## Figure 1. Study 2 – Peri PrEP Dosing (n=62)

[figure not shown]
**Objective:** Determine pharmacokinetics of a combination of NRTIs + INSTI in mucosal tissues following on-demand peri-exposure prophylaxis regimen

**Design:** 2 doses of TAF/FTC/EVG/COBI given **24** hours apart

1st dose recorded observed dosing, 2nd dose observed in clinic

Timing of specimen collection begins following 2nd dose

Each participant has 1 biopsy visit and 1 non-biopsy visit (Except Pre-Drug & Arm D)

	All Specimen Visits	Biopsy Visits
Specimens Collected	Blood (2 CPT, 1 EDTA) Urine Penile/Urethral Swabs Cheek Swab	Standard collection + Rectal Swabs (x2) Rectal Biopsies (x10) Aptima Swab-Rectal STI Testing Semen

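### Penile and urethral drug-level swabs have no instruction on recent insertive or oral sex, lubricant or saliva and no described record of it; the 48-hour request covers only the optional semen sample

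*Combined protocol and SAP*

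**What the plan says.** **The 48-hour request.** Under Semen collection, men are asked to avoid ejaculation, lubricant or saliva on the penis, and "having insertive vaginal, anal or oral sex for at least 48 hours prior to semen collection". The same paragraph ends: "If these instructions are not followed, the semen sample can still be accepted". The sample is voluntary and given once: "Participants will also be asked to provide an optional single semen specimen on the day of rectal sampling" (Abstract).

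**The swabs.** Each specimen visit, with or without a biopsy, has the same text: "an oral cheek swab, 1 pre- wet penile swabs and 1 dry penile swab, and a urethral swab will be collected". These are assay specimens: "Biologic specimens collected after the screening visit will be transferred directly to CDC for measurement of study drug levels" (Biologic specimens). Figure 1 gives two specimen visits per man in Arms A to C and one in the pre-drug arm and Arm D.

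**The rule for everyone.** "All participants will be asked to abstain from receptive anal intercourse for three days prior to drug dosing and during the study protocol" (Study visits, end of the Arm D text). The reason given there is to limit exposures of the rectal mucosa. Inclusion criterion 9 and the Risk of Genvoya section also name receptive anal intercourse only.

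**After a biopsy.** Men are asked to abstain for 7 days. The Abstract and inclusion criterion 9 call this receptive anal intercourse, the Rigid sigmoidoscopy and biopsies section calls it anal intercourse, and the text after Arm D says intercourse without a qualifier.

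**Records.** High-risk behaviour is monitored at visits for HIV safety (Risk of Genvoya). Case report forms take behavioural data at study entry (Subject Privacy and Data Confidentiality).

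**The concern.** The study exists to describe drug levels at body sites of possible HIV exposure, and the penile surface and urethra are two of the sampled sites. The protocol guards the rectal site against recent contact, and asks semen donors to avoid contact at the penis. It describes nothing comparable for the penile and urethral swabs.

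A man who follows every written instruction could have insertive or oral sex, or use lubricant, shortly before such a swab. The swab could then plausibly be wiped, diluted, or carry a partner's fluid. The Abstract says that tenofovir plus emtricitabine is recommended as PrEP for MSM. A partner on PrEP could therefore carry emtricitabine, and tenofovir if the assay picks it up (the Lay Summary names the alafenamide form).

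Each time point will have 3 to 8 men, so one or two affected swabs could move a summary. Without a timed record, nobody could say afterwards which swabs those were.

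**Working it through.** **1. Reproduce the plan's totals.**
- Maximum enrolment (pre-drug, A, B, C, D): 6 + 16 + 16 + 16 + 8 = 62, as stated.
- Completers: 3 + 8 + 8 + 8 + 4 = 31, as stated under Study Population. The 3 comes from the pre-drug arm, where "enrollment for this Arm will close once 3 men complete their biopsy visit"; the 8 and 4 come from the Arm A to C and Arm D headings.

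**2. Count swab sets among completers.**
- Pre-drug 3 × 1, Arms A to C 24 × 2, Arm D 4 × 1: 3 + 48 + 4 = 55.
- On a biopsy day, when semen may be given: 3 + 24 + 4 = 31.
- Not on a biopsy day: 55 − 31 = 24, which is 24/55 = 43.6%.

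**3. Share without the semen-linked request.** Let f be the proportion of men who give semen. The protocol gives no figure for f, so the values below are assumptions.
- Reading 1, request tied to semen only: (55 − 31f)/55.
- Reading 2, also crediting the unqualified 7-day post-biopsy bar to insertive intercourse. This reaches visit 5 in groups A.1, B.1 and C.1, 3 × 4 = 12 sets, all non-biopsy and so not counted twice: (55 − 12 − 31f)/55.

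| f (assumed) | Reading 1 | Reading 2 |
|---|---|---|
| 0 | 55 sets, 100% | 43 sets, 78.2% |
| 0.25 | 47.25 sets, 85.9% | 35.25 sets, 64.1% |
| 0.50 | 39.5 sets, 71.8% | 27.5 sets, 50.0% |
| 0.75 | 31.75 sets, 57.7% | 19.75 sets, 35.9% |
| 1 | 24 sets, 43.6% | 12 sets, 21.8% |

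More than half of the sets lack the request only if f is below 27.5/31 = 88.7% (reading 1) or below (27.5 − 12)/31 = 50% (reading 2).

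Reading 2 gives partial cover at best. The post-biopsy bar mentions neither lubricant, saliva nor oral sex, and in A.1 it starts 48 − 2 = 46 h before visit 5.

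**4. Length of the extra request if extended to all swab visits.** Take the union of the 48 h before each specimen visit, in hours from the clinic dose.
- Arm A (visits at 2 and 48 h): −46 to 48, 94 h.
- Arm B (4 and 72 h): −44 to 4 and 24 to 72, 96 h.
- Arm C (24 and 96 h): −24 to 24 and 48 to 96, 96 h.
- Arm D and pre-drug: one visit, 48 h.

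**The case against.** The case on the other side is substantial, and much of it stands.

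- **The request gives no reason.** It also bars ejaculation, which fits semen quality. The protocol does not itself say that sex or lubricant spoils a penile swab. This stands: the mechanism is plausible but inferred.
- **No harm is quantified.** The documents give no frequency of contact, no carry-over and no dilution. A partner on the PrEP regimen in the Abstract would not supply elvitegravir or cobicistat, two of the four analytes in the Lay Summary. This also stands.
- **Other restrictions and queries exist.** A reader might infer that most swabs are taken with no restriction on sexual contact and no record of it. The documents do not support that. Receptive anal intercourse is restricted for all, the post-biopsy bar may reach 12 of the 24 non-biopsy sets, high-risk behaviour is monitored at visits, and the share depends on an unstated donation rate. The case report forms are not in the documents, so their content cannot be declared absent.
- **No two fixed conditions.** A reader might infer that donors are swabbed under a binding rule, other men under none, and that the two cannot be separated. But the request is not enforced, and donors can be identified by the specimen and the $20 payment. Each of the six time points in Arms A to C has 4 biopsy and 4 non-biopsy men, so the mix of potential donors does not differ across them by design. Actual exposure, not donor status, is what would be unknown.
- **Overlapping windows.** A donor in A.2 at 48 h has a window that spans visit 4 at 2 h. It does not cover the 48 h before visit 4, so the count is unchanged.

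None of this supplies an instruction or an exposure time for the penile and urethral swabs.

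**Conclusion.** The point holds as a gap in specimen preparation and recording. No instruction on insertive or oral sex, lubricant or saliva, and no timed, swab-specific record, is described for swabs taken at all 55 planned specimen visits. The 48-hour request reaches at most 31 of the 55 sets, and then only as an unenforced request; 24 sets (44%) lack it whatever the donation rate. At 25% to 75% donation the uncovered share is 86% to 58%, or 64% to 36% if the post-biopsy bar is credited. Whether this is a majority depends on two things the protocol leaves open: semen uptake and the meaning of the post-biopsy wording.

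The figures assume the planned 31 completions, and count a set as covered only when the 48 h before it is covered (relaxed in reading 2 for the 12 post-biopsy sets). They say nothing about how many swabs would be affected or by how much. A claim that penile or urethral levels will be biased, or that time points in Arms A to C are not comparable, would go beyond the documents. This is a worthwhile, inexpensive improvement.

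**What to change.** 1. Extend the existing semen wording on lubricant, saliva and insertive or oral sex to every visit with penile or urethral swabs. Make it an unenforced instruction, not an eligibility criterion.
2. Give it at visit 2, and at screening in the pre-drug arm. The gap between visits 2 and 3 is not fixed, and in Arm A the first 48-hour window opens 46 h before the clinic dose, 22 h before the home dose. A reminder through the existing retention contacts would therefore help.
3. At each such visit, record the time of last insertive or oral sex, and of last lubricant or saliva use on the penis: two case report form questions.
4. Keep every swab. Add a sensitivity summary of penile and urethral levels, and of cheek levels for oral sex, without the exposed swabs.
5. Separately, reconcile the post-biopsy abstinence wordings in the Abstract, inclusion criterion 9, the text after Arm D, and the Rigid sigmoidoscopy and biopsies section.

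**Cost.** No new procedure, staff or participants. Men are asked for about 94 to 96 h of extra abstinence in Arms A to C and 48 h in Arm D and the pre-drug arm; this is a real burden where 31 of 62 are expected to complete. The sensitivity summary will rest on fewer than the 3 to 8 men per time point wherever swabs are dropped. If the extra request is unwelcome, step 3 alone would make affected swabs identifiable.
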